9.13.7 Clinical Laboratory Data

All reported clinical laboratory test results will be assigned to one of the time points using the time windows specified in the table below.

Table 1 - Analysis Time Windows

Time point	Time Window
Visit 1	Last value prior to start of study treatment (i.e. ≤study day 1)
Actual EoT	Study day of last dose (28 days prior to EoT - 14 days post EoT)
12 weeks (day 85 post EoT)	57 – 112 post EoT

Mean changes from baseline to each post-baseline visit will be summarized descriptively.

Laboratory data values collected during the treatment period will be categorized as low, normal, or high based on reference ranges used in this study. The number and percent of patients who experience post-baseline shifts during treatment in clinical laboratory values from low/normal to high and high/normal to low based on the reference range will be summarized.

Additional details of the analyses of clinical laboratory data will be specified in the SAP.

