In total, there will be at least four study visits. Patients who prematurely discontinue the study should return to the site to document EoT data.

The schedule of the study procedures is presented in table 4.1.

Table 4.1 – Program activities

| Assessment/ Procedure (only available data to be collected; no diagnostic or monitoring procedures to be applied to the patients apart from those of routine clinical practice) | Visit 1 | Treatment period | | Post-treatment period | |
|--|---------|------------------------------|------------------------|-----------------------|-----------------|
| | | EoT (on-treatment visits) | Safety Follow-up visit | SVR12 | Follow-up visit |
| Written patient authorization form | X | | | | |
| Inclusion/Exclusion Criteria | X | | | | |
| Demographic information | X | | | | |
| IL28B | X | | | | |
| Relevant CHC disease characteristics | X | | | | |
| Liver fibrosis stage | X | | | | |
| CHC treatment history | X | | | | |
| HCV genotype and subtype | X | | | | |
| HCV RNA samples | X | X | | | X |
| Clinical chemistry and hematology | X | X | | | X |
| ABBVIE REGIMEN initiation documentation | X | | | | |
| ABBVIE REGIMEN adherence | X | | X | | |
| Concomitant medication | X | X | | | X |
| Relevant medical history, co-morbidities | X | | | | |
| SAE, non-serious AE and pregnancy reporting | X | X | X | X | X |

Time windows for reported clinical laboratory test results are described in the table 4.2.

Table 4.2 – Analysis time windows

| Time point | Time Window |
|------------------|--|
| Visit 1 | Last value prior to start of study treatment (i.e. \leq study day 1) |
| EoT ¹ | Study day of last dose (from study day 56 to study day 98) |
| SVR12 | last value between 57 and 112 days post the study day of last dose |

¹ The EoT time window will not be used for the target population analyses, actual collected EoT visit will be presented in this case even if $EoT \leq$ study day 55 (less than 8 weeks).

P16-253 (CITRIN) _ STATISTICAL ANALYSIS PLAN _ FINAL 2.0 _ 16 Mar 2018

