To avoid the multicollinearity problem all possible explanatory variables will be examined using following SAS script:

```
ods graphics on;
PROC CORR data=<dataset> plots=all;
VAR <variables>;
RUN;
ods graphics off;
```

Statistical significant correlated variables with correlation coefficient ≥ 40 should be considered and managed. All solutions about an explanatory variables choosing will be of exploratory nature, data driven, and will be described with presenting of results of the "PROC CORR" SAS procedure.

Backward selection procedures will be applied to generate the final MLR models esing the SAS procedure LOGISTIC with statement SELECTION = BACKWARD and SLENTRY = 0.05. A p-value <0.05 condition will be used for the covariates to stay in the model in a backward elimination step.

Odds ratio with 95% Wild CI, p-values will be presented for each predictor.

All data for effectiveness analyses will be listed in separate listings (for each effectiveness analyses endpoint).

10 Safety analysis

Safety analysis will be conducted on *the safety population (SP)*.

The following parameters will be analyzed:

- study drug exposure;
- adverse events;
- pregnancies;
- clinical laboratory evaluations.

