10.4 Clinical laboratory evaluations

Clinical laboratory evaluations include the following parameters:

- hematology results;
- blood chemistry results.

The following parameters, which are evaluated at each study visit, will be analyzed in tables and presented in listings:

- hematology:
 - hemoglobin;
 - platelets;
 - prothrombin time (seconds);

P16-253 (CITRIN) _ STATISTICAL ANALYSIS PLAN _ FINAL 2.0 _ 16 Mar 2018

- prothrombin time (INR);
- blood chemistry:
 - ALT;
 - AST;
 - GGT;
 - total bilirubin;
 - alpha-1-fetoprotein;
 - albumin;
 - creatinine;
 - creatinine clearance.

The results of clinical laboratory evaluations statistical analysis will be represented in accordance with section 7.1 as the following outputs:

- tables with descriptive statistics of measurement values and changes from baseline (visit 1);
- frequency tables of out of range and clinically significant evaluates will be presented;
- shift tables based on clinical evaluation of measurements at visit 1.

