10.5 Other safety measures

No other safety measures will be analysed in this study.

P16-253 (CITRIN) _ STATISTICAL ANALYSIS PLAN _ FINAL 2.0 _ 16 Mar 2018

11 Pharmacokinetics

No pharmacokinetic and pharmacodynamic parameters will be analyzed in this study.

12 Other analyses

No other analyses will be performed in this study.

13 Interim analyses and data monitoring

No interim analysis is planned for this study.

14 Technical details and reporting conventions

Statistical analysis will be performed using SAS 9.4. One (final) statistical analysis report will be prepared in the Microsoft Office Word (.docx) format after the end of data collection and database lock. The results of statistical analysis will be presented in the form of tables, figures and listings in English.

15 Summary of changes to the Protocol

This SAP is fully consistent with the clinical study Protocol.

16 List of TFLs**16.1 Tables****Subjects Disposition**

Table 1.1 – Subjects Dispositions
Table 1.2 – The reasons of early withdrawal
Table 1.3 – Violation of eligibility criteria

Demographics and anthropometric characteristics

Table 1.4.1 – Demographics and anthropometric characteristics [CP]
Table 1.4.2 – Demographics and anthropometric characteristics (prior treatment groups) [CP]
Table 1.4.3 – Demographics and anthropometric characteristics (treatment-experienced groups) [CP]
Table 1.4.4 – Demographics and anthropometric characteristics (Child Pugh score groups) [CP]
Table 1.4.5 – Demographics and anthropometric characteristics [TP]
Table 1.4.6 – Demographics and anthropometric characteristics [SP]
Table 1.5.1 – CHC disease characteristics [CP]
Table 1.5.2 – CHC disease characteristics (prior treatment groups) [CP]
Table 1.5.3 – CHC disease characteristics (treatment-experienced groups) [CP]
Table 1.5.4 – CHC disease characteristics (Child Pugh score groups) [CP]
Table 1.5.5 – CHC disease characteristics [TP]
Table 1.5.6 – CHC disease characteristics [SP]

CHC disease characteristics

Table 1.6.1 – Liver fibrosis stage [CP]
Table 1.6.2 – Liver fibrosis stage (prior treatment groups) [CP]
Table 1.6.3 – Liver fibrosis stage (treatment-experienced groups) [CP]
Table 1.6.4 – Liver fibrosis stage (Child Pugh score groups) [CP]
Table 1.6.5 – Liver fibrosis stage [TP]
Table 1.6.6 – Liver fibrosis stage [SP]

Liver fibrosis stage

P16-253 (CITRIN) _ STATISTICAL ANALYSIS PLAN _ FINAL 2.0 _ 16 Mar 2018

Alcohol consumption

Table 1.7.1 – Alcohol consumption [CP]

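### The SAP's fixed EoT laboratory window and visit-based shift tables keep early-stop and mid-course values out of the safety laboratory tables, contrary to the protocol and undeclared

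*SAP*

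**What the plan says.** **Protocol, section 9.13.7.** Table 1 has three laboratory time points: Visit 1, actual EoT and 12 weeks after EoT. The EoT entry is "Study day of last dose (28 days prior to EoT - 14 days post EoT", so it moves with the patient's own last dose. The text then plans a summary of "post-baseline shifts during treatment in clinical laboratory values from low/normal to high", and the reverse, on values collected in the treatment period and classed as low, normal or high by reference range.

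**SAP, section 4.1, Table 4.2.** The EoT entry is "Study day of last dose (from study day 56 to study day 98". Footnote 1 gives one exemption: "The EoT time window will not be used for the target population analyses".

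**SAP, section 10.** "Safety analysis will be conducted on" the safety population, which is everyone with at least one dose. Section 10.4 promises "tables with descriptive statistics of measurement values and changes from baseline (visit 1", frequency tables of out-of-range and clinically significant results, and "shift tables based on clinical evaluation of measurements at visit 1".

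**SAP, section 18 (shells).** Tables 3.3.1 to 3.3.3 are headed for the safety population and have rows for Visit 1, EoT and SVR12 only. The categories are Normal, Abnormal NCS and Abnormal CS (not clinically significant, clinically significant). The chemistry tables copy these shells. No laboratory table is listed for the target population.

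**SAP, section 15.** "This SAP is fully consistent with the clinical study Protocol".

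**The concern.** The footnote shows that early stopping was foreseen, but the exemption is attached to a population that has no laboratory tables. Patients who stop early are in the safety population, and the SAP asks them to return so that EoT data can be documented. The window then excludes the sample that the visit produces.

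The second departure is independent of the first. The protocol's shift summary is defined by the treatment period. The SAP's is defined by visit and by the investigator's judgement of clinical significance. Extra visits may be made when clinically necessary, and samples from them have no row.

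Tolerability is a stated secondary objective in a cirrhotic population. Samples taken at early stopping or for a clinical reason are plausibly among the most informative on safety. With 60 patients, one or two missing from a table matter to a descriptive account. A reader of section 15 would not know that either rule had changed.

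**Working it through.** **Inputs.** Protocol window: actual EoT -28 to +14 days (protocol Table 1). SAP windows: Visit 1 up to day 1, EoT days 56-98, SVR12 from 57 to 112 days after last dose (SAP Table 4.2). Planned course: 12 weeks. L is the study day of last dose.

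**Step 1: reproduce the SAP figure.** Planned L = 12 × 7 = 84. The protocol rule gives 84 - 28 = 56 and 84 + 14 = 98. Days 56-98 are the protocol rule frozen at a day-84 last dose.

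**Step 2: two readings of the SAP entry.** It can limit the sample date (reading A) or the day of last dose (reading B). Windows below start no earlier than day 2, the first post-baseline day.

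| L | Protocol window | Overlap with 56-98 (reading A) | EoT value possible under reading B? |
|---|---|---|---|
| 28 | 2-42 | none | no |
| 41 | 13-55 | none | no |
| 42 | 14-56 | day 56 only | no |
| 55 | 27-69 | 56-69, 14 of 43 days | no |
| 70 | 42-84 | 56-84, 29 of 43 days | yes |
| 84 | 56-98 | 56-98, 43 of 43 days | yes |

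For L ≤ 55 the stopping-day sample is excluded on both readings. Under A, only a post-treatment sample from day 56 on could stand in as EoT. For L ≤ 41 that is at least 56 - 41 = 15 days after treatment, outside the protocol window. Under B there is no EoT value at all. For L = 70 the two readings disagree, so the conclusion is limited to L ≤ 55.

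**Step 3: mid-course values.** Visit 1 ends at day 1. EoT under reading A begins at day 56. The earliest possible SVR12 value is on day 1 + 57 = 58. Days 2-55 fall in no time point. Under reading B the EoT row still has no place for an extra-visit value on those days. For a day-84 completer this is 55 - 2 + 1 = 54 of 84 - 2 + 1 = 83 on-treatment days, or 65%. In that patient the protocol's EoT window also starts at day 56, so the fixed window is not the cause. The values are lost because the during-treatment shift summary was replaced.

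**Step 4: how many patients.** Neither document gives an early-stop rate for this study. The only related figure is the cited 60-patient trial of the same regimen, in which all 60 completed (protocol section 7.0). The Clopper-Pearson 95% upper limit for 0 of 60 is 1 - 0.025^(1/60) = 5.96%, and 0.0596 × 60 = 3.6 patients. This is for any non-completion; stops by day 55 would be a subset. Routine practice could differ. The number of extra-visit samples is not given either.

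**The case against.** The strongest case for leaving the plan alone has five parts.

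- **The values are not lost.** Listings 4.4 and 4.5.1 cover hematology and chemistry, and nothing limits them to the windows. The protocol's adverse event definition includes abnormal laboratory findings. Treatment-emergent events are tabulated on the safety population to 30 days after dosing, with no day-56 limit, and Table 3.1 tabulates reasons for deviating duration. This stands, and it limits the harm. But the adverse event route needs an investigator to report the finding, and a listing is not a summary.
- **The protocol lets the SAP add detail on laboratory analysis.** True, but replacing a patient-specific anchor with calendar days, and a reference-range shift with a clinical judgement, changes the rule. Section 15 is the place to say so.
- **The protocol's shifts may also be limited to its time points,** since section 9.13.7 opens by assigning all results to one of them. Its shift sentence, however, refers to values collected during the treatment period, not at visits.
- **SAP 10.4 speaks of each study visit.** The shells nevertheless provide only three rows.
- **The impact may be nil.** If nobody stops by day 55, the window costs nothing in practice. That is possible; the shift summary and section 15 would still need correcting.

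Three stronger inferences are tempting, and the documents do not support them. One is that the fixed window explains every missing value before day 56; Step 3 shows that this fails for day-84 completers. Another is that no table uses the upper limit of normal recorded for ALT and AST; SAP 10.4 promises out-of-range frequencies, which need reference limits. The third is that the shift table is defective because a patient clinically significantly abnormal at baseline cannot move higher; the protocol's low/normal/high scheme has the same ceiling.

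**Conclusion.** The point holds, and the plan should be changed, as a matter of safety reporting. Two undeclared departures from protocol section 9.13.7 stand:

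1. A safety-population patient with last dose by day 55 has no stopping-day EoT value in any laboratory table. This does not depend on how Table 4.2 is read. The partial-overlap counts do: they assume that days 56-98 limit the sample date.
2. Extra-visit values on days 2-55 enter no laboratory table for any patient, because visit-based clinical-evaluation shifts replace the during-treatment reference-range shifts. This rests on the shells being the complete set of laboratory tables.

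The consistency statement in SAP section 15 is therefore wrong. The number of patients affected cannot be computed from the documents and may be small; 3.6 of 60 is an upper confidence limit borrowed from another trial, not an estimate for this one. The primary SVR12 result is unaffected, since Table 4.2 is introduced as governing laboratory test results and the finding concerns safety tables only.

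**What to change.** 1. In SAP Table 4.2, define EoT for safety-population laboratory tables by the protocol window around the actual last dose, -28 to +14 days.
2. In SAP 10.4, restore the protocol's low/normal/high shift summary for all analytes. Use every post-baseline on-treatment value regardless of visit window, and state the day on which the treatment period ends. Keep the existing tables and listings.
3. Correct section 15 so that it declares any departure that remains.

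Item 1 recovers early-stop samples but not mid-course ones; item 2 is needed for those. A table of worst on-treatment ALT and AST as multiples of the upper limit of normal would be a reasonable extra, but neither document plans it and the point does not depend on it.

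The cost is SAP wording and one added summary from data already collected, with no new visits. SAP section 2 allows revision before database soft lock; after that, the clinical study report can explain the change. The drawback is sparse cells at 60 patients and dependence on how often each site samples. Albumin and prothrombin time will be thinnest, because protocol section 9.8 does not list them for on-treatment visits. A footnote should say this.

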4.1 Sample size¹

60 patients will be included in this descriptive study without any prior sample size calculation.

4.2 Randomization and blinding

This study is observational with one treatment group. Randomization and blinding procedures are not applicable.

4.3 Planned analyses

The only final statistical analysis report will be performed for this study.

No analyses for DMC meetings and no interim analysis are planned in the study.

5 General considerations

Study Day will be calculated from the reference start date, and will be used to show start/stop day of assessments and events.

Reference start date is defined as the day of the start treatment (“EXSTDTC” variable from “EX” domain of the database).

If the date of the event is on or after the reference date then

study day = (date of event – reference date) + 1.

If the date of the event is prior to the reference date then

study day = (date of event – reference date) – 1.

Baseline is defined as the measurement taken on Visit 1.

6 Analysis populations

The target population (TP) – all patients with signed written Patient Authorization, who fulfill the eligibility criteria. Patients who prematurely discontinue earlier than ≤study day 55 will be used in analyses on the target population with actual EoT time point without windowing conventions adjustment for EoT.

The core population (CP) – all patients of the TP, who have started and received the treatment combination recommended in the current local label for their disease characteristics. Patients with EoT ≤ study day 55 (less than 8 weeks) will be excluded from the CP (these patients will be included to the NCP).

The safety population (SP) – all patients who received at least one dose of the ABBVIE REGIMEN.

The non-core population (NCP) – patients not receiving the treatment recommended in the local label.

The core population with sufficient follow-up data (CPSFU) – all CP patients, who fulfill one of the following criteria:

- evaluable HCV RNA data within the SVR12 time window;

¹ This section is based on the section 9.1.1 “Study Size” of clinical study Protocol.

P16-253 (CITRIN) _ STATISTICAL ANALYSIS PLAN _ FINAL 2.0 _ 16 Mar 2018

- a HCV RNA value ≥ 50 IU/mL at the last measurement post-baseline (i.e. no virological response achieved at the last measurement on-treatment or post-treatment);
- HCV RNA <50 IU/mL at the last measurement post-baseline, but no HCV RNA measurement on the SVR12 visit due to reasons related to safety (e.g. dropped out due to AE) or incomplete efficacy information (e.g. virologic failure such as relapse is reported in the eCRF but date and value of the corresponding HCV RNA test is missing).

In this way, only patients who had virological response at their last on-treatment or post-treatment measurement, but had no HCV RNA measurements within the SVR12 time window for reasons not related to safety or effectiveness (e.g. lost-to-follow-up or patient not willing to perform an additional HCV RNA test on the SVR12 visit) will be excluded from this analysis.

Figure 6.1 illustrates the rule of patient's allocation in the core population with sufficient follow-up data (CPSFU).

[figure not shown]

Figure 6.1 – The core population with sufficient follow-up data (CPSFU) allocation

7 Statistical considerations

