9.13 Data Analysis

9.13.1 Analysis Population, Time Windows and Handling of Missing Data

The target population (TP) is defined as all patients who fulfill the inclusion/exclusion criteria. The core population (CP) is defined as all patients of the TP, who have started the treatment combination recommended in the current local label for their disease characteristics. Patients not receiving the treatment recommended in the local label will be summarized in the non-core population (NCP). In addition, the core population with sufficient follow-up data (CPSFU) is defined as all CP patients, who fulfil one of the following criteria:

- (1) evaluable HCV RNA data ≥ 84 days after the last actual dose of the ABBVIE REGIMEN (i.e. data within the SVR12 time window)

- | (2) a HCV RNA value ≥ 50 IU/mL at the last measurement post-baseline (i.e. no virological response achieved at the last measurement on-treatment or post-treatment)
- | (3) HCV RNA < 50 IU/mL at the last measurement post-baseline, but no HCV RNA measurement ≥ 84 days after the last actual dose of the ABBVIE REGIMEN due to reasons related to safety (e.g. dropped out due to AE) or incomplete efficacy information (e.g. virologic failure such as relapse is reported in the eCRF but date and value of the corresponding HCV RNA test is missing). This means only patients who had virological response at their last on-treatment or post-treatment measurement, but had no HCV RNA measurements ≥ 84 days post-treatment for reasons not related to safety or effectiveness (e.g. lost-to-follow-up or patient not willing to perform an additional HCV RNA test ≥ 84 days post-treatment) will be excluded from this analysis.

The Safety Population (SP) is defined as all patients who received at least one dose of the ABBVIE REGIMEN.

In accordance with the non-interventional nature of the study all HCV RNA measurements will be performed at the sole discretion of the physician and all HCV RNA measurements have to be entered into the eCRF. All recorded HCV RNA values will be assigned to appropriate time points (Visit 1, additional on-treatment visits (if any), EoT visit, 30 days safety follow-up visit and SVR 12 follow-up visit). The time windows for the assignments will be specified in the statistical analysis plan (SAP).

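### SAP section 6 drops the Protocol's 84-day limit from the CPSFU definition; the only SVR12 day limits in the SAP text are a laboratory window of days 57–112

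*SAP*

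**What the plan says.** Protocol 9.13.1 defines the CPSFU with a limit of 84 days after the last actual dose, used four times: in criterion 1, in criterion 3, and twice in the sentence on who is excluded. Criterion 1 also explains the term, asking for evaluable HCV RNA at ≥ 84 "days after the last actual dose of the ABBVIE REGIMEN (i.e. data within the SVR12 time window". No upper limit is given. For assigning HCV RNA values to visits, the same section says: "The time windows for the assignments will be specified in the statistical analysis plan (SAP".

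SAP section 6 repeats the definition without any day count:

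- Criterion 1: "evaluable HCV RNA data within the SVR12 time window".
- Criterion 3: "but no HCV RNA measurement on the SVR12 visit due to reasons related to safety".
- Exclusion sentence: patients who "had no HCV RNA measurements within the SVR12 time window for reasons not related to safety or effectiveness", with the example of a "patient not willing to perform an additional HCV RNA test on the SVR12 visit".

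The only SVR12 row with day limits in the SAP text is in Table 4.2 of SAP 4.1: "last value between 57 and 112 days post the study day of last dose". The table is introduced with "Time windows for reported clinical laboratory test results are described in the table 4.2". In Protocol 9.13.7 the same 57–112 laboratory window was labelled as 12 weeks; the SAP relabels it SVR12.

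SAP 3.2 keeps the 84-day minimum for the primary variable. SAP section 9 and the shells for the effectiveness percentages say only 12 weeks. SAP section 15 declares no departure from the Protocol.

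**The concern.** The Protocol left the HCV RNA windows to the SAP, and the SAP text does not supply them. Its table of contents lists a section 5.2 on windowing, but the body has none. A programmer who needs day limits for the SVR12 window in section 6 will find one row with that name, and it is a laboratory window that opens 27 days too early and closes at day 112.

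Table 4.2 does not look confined to laboratory summaries. Its footnote exempts target-population analyses from the EoT window, yet laboratory summaries are planned only in the safety population (SAP 10 and 10.4). The day-55 cut-off in that footnote also reappears in section 6 to define the CP. Both facts concern the EoT row, but they make it reasonable to carry the SVR12 row over to HCV RNA as well.

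Two kinds of patient would be misplaced:

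- **Early test only.** A responder whose only post-treatment test falls on days 57–83 enters the CPSFU. The Protocol excludes that patient unless the later test is missing for a safety or effectiveness reason. If SVR12 is still derived by SAP 3.2, the patient then has missing SVR12 and counts against the CPSFU rate, although the CPSFU exists to leave such patients out.
- **Late test only.** A responder tested only after day 112 is dropped, although the Protocol includes that patient.

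All effectiveness analyses are repeated in the CPSFU, and the shell titles (though not the list of tables) call both CPSFU percentage tables the main analysis.

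**Working it through.** **1. Text comparison.** Uses of the 84-day limit in the CPSFU definition: Protocol 9.13.1, four; SAP section 6, none. Two became a reference to the SVR12 time window and two a reference to the SVR12 visit.

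**2. Membership under each rule.** Protocol rule: a test at day ≥ 84, or last HCV RNA ≥ 50 IU/mL, or a safety/effectiveness reason for the missing test. SAP rule read by label: a test on days 57–112, or either of the same two alternatives. Comparing the rules for every day from 1 to 199 gives:

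| Only post-treatment test | Protocol | SAP by label |
|---|---|---|
| < 50 IU/mL, no such reason, day ≤ 56 | out | out |
| < 50 IU/mL, no such reason, days 57–83 | out | **in** |
| < 50 IU/mL, no such reason, days 84–112 | in | in |
| < 50 IU/mL, no such reason, day ≥ 113 | in | **out** |
| ≥ 50 IU/mL, or such a reason, any day | in | in |

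The window has 112 − 57 + 1 = 56 days: 84 − 57 = 27 before the Protocol limit and 112 − 84 + 1 = 29 that meet it.

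**3. Interval method.** Clopper-Pearson, as both documents specify. When all n respond, the lower limit is 0.025^(1/n). For n = 60 this is 94.0%, which reproduces the 94.0–100% quoted in Protocol 7.0 for the earlier 60-patient study.

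**4. Early tests.** Assumed: 60 CP patients (the planned study size), k of them negative only on days 57–83 without a safety or effectiveness reason, all others responders at ≥ 84 days. CPSFU rate (95% CI):

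| Reading | k = 1 | k = 3 |
|---|---|---|
| Protocol rule | 59/59 = 100% (93.9–100) | 57/57 = 100% (93.7–100) |
| Section 6 by label, SVR12 by SAP 3.2 | 59/60 = 98.3% (91.1–100.0) | 57/60 = 95.0% (86.1–99.0) |
| 57–112 also used to derive SVR12 (stated nowhere) | 60/60 = 100% (94.0–100) | 60/60 = 100% (94.0–100) |

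With three virologic failures among the 60 and k = 3, the first two rows become 54/57 = 94.7% (85.4–98.9) and 54/60 = 90.0% (79.5–96.2).

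**5. Late tests.** With three responders tested only after day 112 and no failures, the Protocol gives 60/60 (94.0–100) and the label reading 57/57 (93.7–100). With three failures as well, 57/60 = 95.0% (86.1–99.0) becomes 54/57 = 94.7% (85.4–98.9).

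**6. Effect on the CP.** None while SVR12 follows SAP 3.2. If days 57–112 also derived SVR12, each day 57–83 negative would move from missing to response: 1/60 = 1.7 percentage points per patient.

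**The case against.** The best defence is that the term is already defined. The Protocol equates the SVR12 time window with 84 days or more, the SAP is written from the Protocol and says it is consistent with it, and SAP 3.2 keeps the 84-day minimum. Table 4.2 is scoped to laboratory results by its introduction, by the SAP revision history and by Protocol 9.13.7; SAP 10.4 does not list HCV RNA, and both activity tables show HCV RNA separately from chemistry and hematology. An analyst who reads all of this would apply the right rule. That stands, and it is why this is an ambiguity and not a stated change of rule. It does not remove the problem: SAP 3.2 defines an endpoint and names no window, and section 6 uses the label of Table 4.2 without saying that the table does not apply.

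The 95.0% figure needs a mixed reading: the label for membership and 84 days for the endpoint. Under either uniform reading the k = 3 example gives 100%. The CPSFU table without missing SVR12 would also return 57/57, and the missing-SVR12 row and HCV RNA listing would let a reader trace the patients. All true. Yet the mixed reading is what results from following section 6 by label and SAP 3.2 as written.

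Late first tests should be uncommon, since observation is planned for up to 12 weeks after treatment, and their effect is small. A positive after day 112 would not vanish either: relapse in SAP section 9 has no window. If the window also derived SVR12, such a patient with an in-window negative could meet both definitions.

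The omission of 84 days in SAP section 9 is weaker evidence alone, because Protocol 9.9.1 is equally loose while 9.13.4 gives the day rule. Finally, Figure 6.1 illustrates CPSFU allocation and Figure 9.1 the SVR12 categories. Neither was available, and either may state the limit.

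**Conclusion.** The point holds for the SAP text. Section 6 loses all four statements of the 84-day limit, no HCV RNA window replaces them, and the only SVR12 row with day limits conflicts with the Protocol at both ends. Read by label, CPSFU membership changes only for patients whose last HCV RNA is below 50 IU/mL and who have no safety or effectiveness reason for the missing test.

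In the worked example the cost is 1.7 percentage points for one early-tested patient and 5.0 points for three, with the lower confidence limit falling from 93.7% to 86.1% for three. Late-tested responders barely move the rate. These figures rest on an assumed 60 CP patients and assumed counts; the actual number is unknown and could be zero. The Protocol's primary CP analysis is unaffected unless the laboratory window is also used to derive SVR12. This should be fixed, but it does not threaten the primary result. Confidence is medium because the two figures were not available.

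**What to change.** 1. In SAP section 6, restore the Protocol's limit of at least 84 days after the last actual dose, with no upper bound, at all four places: criterion 1, criterion 3, and twice in the exclusion sentence.
2. In SAP section 9 and the effectiveness shells, restore the timing of SAP 3.2 and Protocol 9.13.4: the single last HCV RNA at least 84 days after the last actual dose.
3. State that the SVR12 row of Table 4.2 applies to chemistry and hematology only.
4. Check that Figures 6.1 and 9.1 follow the same rule.

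If a different HCV RNA window is intended, state it in days and record it in SAP section 15 as a change from the Protocol.

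The cost is SAP wording, shell labels and the population-flag code. The Protocol requires every HCV RNA measurement to be entered in the eCRF, so no new data are needed. SAP section 2 allows revision before soft lock; after that, the rule applied can be explained in the study report.
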